**Title: Tranexamic Acid in Prehospital and In Hospital Civilian Trauma Care in Antifibrinolytic Therapy Study**

**NCT#**

**Date: March 7, 2018**

## **Research Project**

**Title:** The role of pre-hospital Tranexamic Acid (TXA) to improve traumatic hemorrhagic shock outcomes.

Early Prehospital Antifibrinolytic Therapy (EPAT) is a prospective observational and a retrospective comparison cohort study of early administration of TXA. TXA will be administered in the hospital and prehospital setting to trauma patients with associated indices of hemorrhagic shock. The efficacy of hospital and prehospital TXA will be assessed via its effect on mortality, total and types of blood products used, total estimated blood loss and the occurrence of adverse thromboembolic events.

**Purpose:**

To determine if pre-hospital administration of TXA in trauma patients with signs of hemorrhagic shock provides for a statistically significant decrease in mortality, total blood product usage and total estimated blood loss, without a significant increase in thromboembolic complications.

### **Background:**

Trauma is one of the leading causes of death amongst people aged 16-35. First responders have limited resources for resuscitation of hemorrhagic shock. TXA is an anti-fibrinolytic that inhibits the activation of plasminogen to plasmin, an enzyme that dissolves blood clots. It has historically been used to minimize blood loss in planned surgeries such as orthopedic and cardiac surgery, control oral bleeding in patients with hemophilia, and treat heavy menstrual periods. [1,2] An inexpensive pharmacologic agent, TXA may have a practical use in the pre-hospital setting of trauma-related hemorrhage.

The CRASH-2 trial, a 20,000 patient randomized study published in 2010, demonstrated a 1.5% reduction in all-cause mortality at 28 days. [3] This study primarily examined civilian blunt trauma injuries in which TXA was administered within 8 hours of injury. This trial confirmed the safety of TXA in trauma-related injuries given within 3 hours of their traumatic injuries.

At present time, TXA is being widely used in combat related injuries. The MATTERS study published in 2012 examined TXA use in combat injuries requiring at least 1 unit of blood in Afghanistan at the Bastion Role 3 facility. [4] This retrospective, cohort study demonstrated findings supportive of TXA in severely injured, actively bleeding patients. Although there was no overall survival benefit at 24 hours, a survival benefit was seen in patients requiring massive transfusion improving survival at 48 hours by 13.1%.

Early administration of TXA to decrease trauma related mortality has also been established. In 2011, a subgroup analysis of the CRASH-2 Trial proved early treatment with TXA less than one hour from injury resulted in a 2.4% decrease in death. Interestingly, there was a 1.3% increased risk of death due to bleeding in patients who received TXA after 3 hours from injury. [5] Another CRASH-2 economic subset analysis highlighted the fact that TXA can be highly-cost effective. [6]

Applying what we know from these major trials, TXA should have significant benefit in the pre-hospital setting. Two recent small trials have demonstrated that pre-hospital administration of TXA is in fact feasible. [7, 8] By intervening early in trauma related hemorrhage, TXA can improve outcomes and

allocation of resources such as blood product usage, mortality, and length of hospital stay. [6] Hypocoagulopathy contributes to significant mortality in trauma related injuries. To date, there are no prospective trials on the use of TXA in the prehospital setting to help treat trauma-induced coagulopathy. [9] The rationale for early administration of TXA in the pre-hospital setting is to prevent hemorrhagic shock and coagulopathy. This has implications not only for trauma and emergency medicine but in the overall allocation of resources. Furthermore, this may also reduce the number of operating room cases, the number of critical patients, and hospital length of stay.

A recent randomized, double-blinded, placebo-controlled trial studied patients given TXA with moderate to severe traumatic brain injury to see if it prevented progressive intracranial hemorrhage. There was a non-significant trend to decreased intracranial hemorrhage in the TXA group. Though no clinically significant benefit was shown in patients presenting with brain hemorrhage, there may be a role for those who develop coagulopathy after severe brain trauma. [10]

The role of TXA in the pre-hospital setting is still unclear; however its benefits on mortality in the bleeding trauma patient have been established. We hope to elucidate some of these questions and have TXA intertwined in the fiber of management of the trauma patient.

#### **Design: Retrospective Comparison and Prospective Cohort Study**

Four groups of patients will be utilized in this study as follows:

**A: Hospital Group:** this group will receive both doses of TXA according to the draft protocol upon arrival to the participating trauma center. No TXA will be given in the field to this patient grouping. 200 patients shall be enrolled in this group in a prospective observational study format.

**B: Air Transport Group:** This group will receive the first dose of TXA according to the draft protocol on scene or during the flight by a licensed flight RN or licensed flight physician. The second dose of TXA will be administered upon arrival at the participating trauma center. 200 patients shall be enrolled in this group in a prospective observational study format.

**C: Paramedic Group:** These patients will receive their first dose of TXA according to the draft protocol in the field by licensed paramedics from participating agencies. The second dose of TXA will be

administered upon arrival at the participating trauma centers. 200 patients shall be enrolled in this group in a prospective observational study format.

**D: Control Group:** 200 patients, transported by ambulance or by air, with similar injury severity and hemodynamics shall be randomly chosen from the previous five years of the trauma registry at the participating trauma center. These patients shall then be compared to Group A, B and C noted above in a retrospective comparison.

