### **Comparisons:**

Groups A, B and C shall be compared to each other in the following format.

1. Hospital/TXA vs. Air Transport/TXA
2. Hospital/TXA vs. Paramedic/TXA
3. Air Transport/TXA vs. Paramedic/TXA
4. Hospital vs. Control Group to validate results of the CRASH-2 Study

All patients receiving TXA should utilize the same inclusion criteria no matter what group they fall into (excluding the control group) to allow for accurate and consistent comparison. All patients in the control group should meet the same inclusion criteria as the patients who received TXA in groups A, B and C.

Patients who fulfill the inclusion criteria will be administered TXA at the participating trauma center or in the field by trained Paramedics, RNs or Flight Physicians from the participating agencies according to the study protocol. The first dose of the TXA (1gm over 10 minutes intravenous or interosseous drip) shall be administered as soon as possible by the hospital or the participating responder teams. A red colored wristband labeled “TXA” attached to their right wrist and/or TXA written on their chest will identify patients who received TXA. Subsequently, upon arrival at the participating trauma center the patients who received TXA will be identified and re-assessed by the trauma team members for hemorrhagic shock. If the patient still meets inclusion criteria, the TXA will be continued at the participating trauma center (1gm over 8 hours intravenous infusion). Patients that meet the inclusion criteria and were not given TXA because they were brought to the emergency department by agencies other than participating agencies will be assigned to the Group A. Administration of TXA is not anticipated to delay patient transport to participating trauma centers. Currently, TXA is part of the mass transfusion protocol at ARMC for patients in traumatic hemorrhagic shock.

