**Inclusion criteria:**

The hospital and prehospital use of TXA should be considered for all trauma patients that meet **any** of the following criteria:

- Blunt or penetrating trauma with signs and symptoms of hemorrhagic shock.
- Systolic blood pressure of less than 90 mmHg at scene of injury, during air or/and ground medical transport, or on arrival to designated trauma centers
- Any Sustained Blunt or Penetrating injury within 3 hours
- Patients who are considered to be high risk for significant hemorrhage
  - Estimated blood loss of 500 milliliters in the field accompanied with HR >120.
  - Bleeding not controlled by direct pressure or tourniquet.
  - Major amputation of any extremity above the wrists and above the ankles.

[figure not shown]

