**Exclusion criteria:**

- Any patient under 18 years of age.
- Any patient with an active thromboembolic event (within the last 24 hours) – i.e. active stroke, myocardial infarction or pulmonary embolism.
- Any patient with a hypersensitivity or anaphylactic reaction to TXA.
- Any patient more than three-hour post injury.
- Traumatic arrest with > 5 minutes CPR without return of vital signs
- Penetrating cranial injury
- Traumatic brain injury with brain matter exposed
- Isolated drowning or hanging victims
- Documented cervical cord injury with motor deficit

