#### **End Point and Data Analysis:**

##### Primary Outcome

- Mortality at 24 hrs, 48 hrs, and 28 days

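### Hospital-TXA patients enter at the trauma center and pre-hospital-TXA patients before it, and the plan sets no common time zero or rule for deaths before arrival

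*Combined protocol and SAP*

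**What the plan says.** The Design section ties each prospective group to the place of the first dose.

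- **Group A:** "this group will receive both doses of TXA according to the draft protocol upon arrival to the participating trauma center". The Comparisons section adds a route into A, for eligible patients who "were not given TXA because they were brought to the emergency department by agencies other than participating agencies". Both describe patients already at the hospital.
- **Group B:** "This group will receive the first dose of TXA according to the draft protocol on scene or during the flight".
- **Group C:** "These patients will receive their first dose of TXA according to the draft protocol in the field by licensed paramedics".
- **Group D:** sampled at random from five years of the trauma center's registry. Nothing is said about its index time or about patients dead on arrival.

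The primary outcome is "Mortality at 24 hrs, 48 hrs, and 28 days", with no statement of when the clock starts. The Comparisons section lists A vs B, A vs C, B vs C and A vs D. The Design section also says that D will be compared with all three TXA groups.

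The exclusion for "Traumatic arrest with > 5 minutes CPR without return of vital signs" and the three-hour limit are not tied to a moment of assessment.

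On the second dose, the Design section says without condition that B and C receive it on arrival. The Comparisons section makes it conditional: "If the patient still meets inclusion criteria, the TXA will be continued at the participating trauma center".

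**The concern.** Comparisons 1 and 2 (hospital TXA against air and against paramedic TXA) are the listed comparisons that address the stated purpose, the effect of giving TXA before hospital. A death between the scene and the emergency department can never appear in Group A. In B or C the same death may follow the first dose. Whether it is counted decides what is being compared, and the plan leaves that open.

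- **Counted in B and C only:** the pre-hospital groups carry deaths that the comparator cannot carry, and early TXA looks worse than it is.
- **Not counted:** the groups start from the same point, but the result describes only patients who arrive alive. Any in-transit death that TXA prevents is invisible.

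The same choice affects any comparison of B or C with D. B vs C is not affected in this way, since both are dosed before arrival. The Statistical analysis section lists regression but specifies no model and no adjustment for start time or survivor selection.

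**Working it through.** **The plan's own figure.** The plan gives no figure on this point. Its only design figure is 200 per group, from 95% confidence and a 10% margin. For a difference of two proportions at 50%, n = 1.96² × 2 × 0.25 / 0.10² = 192.1, so 193. That is close to 200 and is not called an error. At n = 200 the half-width is 1.96 × √(0.5/200) = 9.8 points.

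**Inputs.** From the Background: a 1.5% reduction in 28-day mortality, and a 2.4% decrease with treatment within one hour. Both are read as percentage points, and both are TXA against no TXA. Assumed, because the documents give neither: q, the share of field-dosed patients who die before arrival (1% to 5%), and m, mortality after arrival (10% to 30%).

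**Case 1: pre-arrival deaths counted in B/C, no drug effect.** Mortality is q + (1−q)m in B/C and m in a group limited to arrivals. The difference is q + (1−q)m − m = q(1−m). In percentage points:

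| q | m = 10% | m = 20% | m = 30% |
|---|---|---|---|
| 1% | 0.9 | 0.8 | 0.7 |
| 2% | 1.8 | 1.6 | 1.4 |
| 3% | 2.7 | 2.4 | 2.1 |
| 5% | 4.5 | 4.0 | 3.5 |

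**Break-even.** The bias equals an effect e when q = e/(1−m).

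- e = 1.5 points: q = 1.7%, 1.9% and 2.1% at m = 10%, 20% and 30%, or about 3 to 4 of 200 patients.
- e = 2.4 points: q = 2.7%, 3.0% and 3.4%, or about 5 to 7 of 200.

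**Cross-check.** Let M = q + (1−q)m be mortality from first contact. The bias is then q(1−M)/(1−q), which is the same quantity because 1−M = (1−q)(1−m). With M (not m) set at 20%, it is 0.8, 1.6, 2.5 and 4.2 points at q = 1%, 2%, 3% and 5%.

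**Case 2: only arrivals counted.** Illustration with assumed values: pre-arrival death is 5% without field TXA and 3% with it, and mortality after arrival is 20% in both.

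- True mortality: 0.05 + 0.95 × 0.20 = 24.0% without, and 0.03 + 0.97 × 0.20 = 22.4% with, a benefit of 1.6 points.
- Arrivals only: 20% against 20%, no benefit.
- Adding back only the B/C deaths: 22.4% against 20%, an apparent harm of 2.4 points.

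The true value lies outside the two results, because the comparator's pre-arrival deaths remain unseen.

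**The case against.** The strongest reply is that the text never says pre-arrival deaths in B and C count. The Comparisons section has dosed patients identified and re-assessed on arrival. If enrollment follows that step, the start points match and the q(1−m) inflation is zero. This stands: a reader might infer that the comparisons do start at different points, but the documents support only that the start is undefined. The gap remains, because the other choice changes what the result means, as Case 2 shows.

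Other stronger readings also go beyond the documents.

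- **All controls arrived alive.** The registry source implies this; nothing states it.
- **The bias exceeds the expected effect.** The plan states no expected effect for early against later TXA. The 1.5 and 2.4 points are TXA against no TXA, and q = 1% reaches neither.
- **Opposing biases make the sign untrustworthy.** Only one bias can be sized here. Low systolic pressure counts "at scene of injury, during air or/and ground medical transport, or on arrival to designated trauma centers", but it is one of several alternative criteria. A patient first hypotensive on arrival could already have qualified in the field.
- **In-transit arrest removes a patient from A only.** The arrest exclusion needs more than five minutes of CPR and no return of vital signs, and it is not limited to one group.

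It is also true that a bias of 1.6 points is about 3 of 200 patients, well inside the 9.8-point half-width. But the bias is systematic and does not shrink as patients are added.

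**Conclusion.** The concern holds as a gap in the definition of the primary comparison. Group A can be entered only at the trauma center, B and C are dosed before it, and no time zero or rule for pre-arrival and dead-on-arrival deaths is given. If pre-arrival deaths count in B/C, comparisons 1 and 2 and B/C vs D are biased against pre-hospital TXA by q(1−m). At q = 2% that is 1.4 to 1.8 points for m from 30% down to 10%, of the same order as the cited TXA effects. The size rests wholly on assumed q and m; below a q of about 1.7% the bias is under 1.5 points throughout that range. If the deaths do not count, this bias disappears, but the result is mortality among patients arriving alive and must be labelled so. The choice has to be made in advance.

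**What to change.** For comparisons 1 and 2 and any comparison of B or C with D:

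- Use one entry point in every group, alive at trauma-center arrival, and exclude dead-on-arrival patients from all groups.
- For analysis purposes, apply the existing arrest and three-hour exclusions at that same point, and start the 24 h, 48 h and 28 day clocks there.
- Do not let group membership depend on receiving the second dose. The Design and Comparisons sections differ on whether that dose is conditional in B and C and must be reconciled.
- State that the result is mortality among patients arriving alive.
- Record and report B and C deaths between field dose and arrival separately. Add a sensitivity analysis that counts them, described as biased against pre-hospital TXA and not as a bound. Where comparator deaths before arrival are unknown, show results over an assumed range.

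The cost is mainly protocol and analysis wording. Injury-to-TXA time, pre-hospital vital signs and EMS-to-ED time are already listed for collection; arrival time and transporting agency are not listed explicitly and may need adding. The downside is that in-transit benefit is not captured in the primary comparison. Group A patients must also still survive from arrival to their first dose, which should be acknowledged.

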### **Data collection:**

Baseline characteristics

- Time of injury to TXA
  - (1st and 2nd dose)
- Demographics: Age, Gender, Race
- Vital Signs: five sets (pre-hospital, during infusion, post-infusion, during second infusion, post-infusion)
  - Heart rate, respiratory rate, body temperature, blood pressure, capillary refill
- Glasgow Coma Scale (pre-treatment, 24 hours, 48 hours)
  - ≤8, 9-12, 13-15

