### **Analysis Measures**

- Survival at 24 hours, 48 hours, and 28 days
- Cause of death (hemorrhage, other causes)
- Mechanism of injury (blunt, penetrating, combination of blunt and penetration, amputation)

- Area of injury
  - Head, chest, abdomen, extremity, multiple areas
- Blood product Used:
  - Packed red blood cells, fresh frozen plasma, platelets, cryoprecipitate.
- Estimated blood loss
  - Pre-hospital and hospital estimate, operating room estimate, and chest tube output
- Number of transfused unit(s) of blood products (<2 units, 2-4 units, >4 units i.e. massive transfusion.
- Time to emergency care: Time from EMS encounter to emergency department (ED), time spent in emergency department, time from ED arrival to operating room.
- Hospital length of stay: Intensive care unit length of stay, discharge disposition
- Ventilator days
- Adverse side effects, thromboembolic, seizures
- Deep venous thrombosis prophylaxis timing
- Result of drug test and medications that may falsely alter patients pulse during the initial evaluation and resuscitation

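### Group A has no transport condition while Groups B, C and D all consist of EMS-transported patients, so comparisons 1, 2 and 4 can include self-presenting patients in A only (minor)

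*Combined protocol and SAP*

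**What the plan says.** The Design section describes four groups of 200.

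- **Group A (Hospital)** is defined by place of dosing: "this group will receive both doses of TXA according to the draft protocol upon arrival to the participating trauma center". It adds "No TXA will be given in the field to this patient grouping". How the patient reached the center is not mentioned.
- **Group B (Air Transport)** has its first dose given "on scene or during the flight by a licensed flight RN or licensed flight physician". **Group C (Paramedic)** has it given by paramedics of participating agencies. Both therefore involve EMS contact.
- **Group D (Control)** carries an explicit transport condition: "200 patients, transported by ambulance or by air, with similar injury severity and hemodynamics shall be randomly chosen", drawn from five years of the trauma registry.

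The Comparisons section lists A against B (1), A against C (2), B against C (3) and A against D (4). It also has one explicit rule that sends patients to A: those who qualify but "were not given TXA because they were brought to the emergency department by agencies other than participating agencies will be assigned to the Group A".

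The Inclusion criteria apply if any one item is met, and one item is low systolic pressure first seen on arrival at the trauma center. No item in the Exclusion criteria concerns mode of arrival.

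Data collection lists vital signs in "five sets (pre-hospital, during infusion, post-infusion, during second infusion, post-infusion". Analysis Measures includes "Time from EMS encounter to emergency department (ED" among the care intervals. Arrival mode appears in neither list.

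**The concern.** The plan applies a transport condition to the controls but not to the group those controls are compared with. An eligible patient who comes in by private vehicle or on foot and is dosed at the center meets A's definition and cannot belong to B, C or D. If such patients are enrolled, A differs from each comparator by a patient type as well as by treatment or its timing. Three of the four comparisons use A, and mortality is the primary outcome.

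Adjusting afterwards would be awkward. A self-presenting patient has no pre-hospital vital signs, and no arrival set before the infusion is listed in their place. The EMS-to-ED interval would be blank and would look like ordinary missing data. An adjusted model using either item would drop these patients from A only; a model using neither would leave the difference in.

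**Working it through.** **1. The groups side by side**

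| Group | Transport stated? | Can a self-presenting patient enter? |
|---|---|---|
| A | No | Yes, nothing prevents it |
| B | Air crew gives first dose | No |
| C | Paramedics give first dose in the field | No |
| D | Ambulance or air only | No |

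The rule on non-participating agencies describes patients brought in by an agency, but it is not worded as the only route into A. It neither admits nor bars self-presenting patients. With eligibility possible on arrival and no relevant exclusion, A is open to them because nothing closes it.

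**2. The plan's own figure**

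Statistical analysis gives 200 per group from 95% confidence and a 10% margin. No event rate is stated, so I assume p = 0.5.

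- Single proportion: 1.96² × 0.25 / 0.10² = 96.04, so 97.
- Difference of two proportions: 1.96² × 0.50 / 0.10² = 192.1, so 193 per group.

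Neither gives exactly 200, though 193 rounded up is plausible. With 200 per group the half-width for a difference is 1.96 × √(0.50/200) = 9.8 points. The present point does not depend on how 200 was reached; the half-width is used only for scale.

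**3. Illustrative shift in A's mortality**

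Shift = share of A that self-presents × mortality difference from A's EMS patients. Neither input is in the documents, so both are assumed: share 2% to 20% (4 to 40 of 200), difference 5 to 15 points in either direction.

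| Share (patients) | 5 points | 10 points | 15 points |
|---|---|---|---|
| 2% (4) | 0.1 | 0.2 | 0.3 |
| 5% (10) | 0.25 | 0.5 | 0.75 |
| 10% (20) | 0.5 | 1.0 | 1.5 |
| 20% (40) | 1.0 | 2.0 | 3.0 |

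At a share of zero the shift is zero. The Background cites a 1.5-point mortality reduction from CRASH-2, the result comparison 4 is meant to validate. The shift exceeds 1.5 points only at a 20% share with a difference of 10 points or more.

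**4. Cost of restricting A**

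To keep 200 after restriction, enroll 200/(1 − share). Without replacement, A has 200 × (1 − share) patients, and the half-width against a group of 200 is 1.96 × √(0.25/n_A + 0.25/200).

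| Share | Enroll to keep 200 | A without replacement | Half-width (points) |
|---|---|---|---|
| 2% | 205 | 196 | 9.8 |
| 5% | 211 | 190 | 9.9 |
| 10% | 223 | 180 | 10.1 |
| 20% | 250 | 160 | 10.4 |

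**The case against.** The strongest reply is that the problem may not exist. The documents never mention private-vehicle or walk-in patients, and the one explicit rule for filling A concerns patients brought by agencies. A reader might infer that every comparison with A does contain such patients. The text supports only that it can. This part of the objection stands in full.

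A reader might also infer that the data plan has no means of adjustment. That goes too far. Mechanism of injury, pre-treatment Glasgow Coma Scale and time from injury to each dose are all collected, and none needs EMS contact. Delay is capped by the three-hour exclusion. A patient who qualified on arrival pressure had a pre-dose pressure measured, even though it is not a listed item. Selecting D by transport mode also implies that the registry holds that field, so it may be recoverable for A if A's patients are in the same registry, which the documents do not say. These items compensate in part. They do not replace a recorded arrival mode or a planned pre-dose arrival set, and the plan names regression without naming covariates.

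On size, the shift is wholly assumed and well inside the 9.8-point half-width. Setting it against the 1.5-point effect makes it look more decisive than it is in a study too small to resolve that effect. This is fair as to scale. What remains is that a difference in composition is systematic, so enrolling more patients under the same rules would not remove it.

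Finally, restriction narrows A and leaves another difference untouched: A draws on non-participating agencies and C on participating ones. That is a separate matter. The narrowing can be met by keeping self-presenting patients in a sensitivity analysis.

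**Conclusion.** The concern holds as a possibility created by the wording, and its severity is minor. A's transport mode is undefined, while D's is restricted and that of B and C is fixed by construction, so comparisons 1, 2 and 4 may not be like with like on a condition the plan itself imposes on the controls. Comparison 3 is unaffected.

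The 0.1 to 3.0 point range rests entirely on the assumed shares and mortality differences, has no known direction, and includes no effect at all if no such patients are enrolled. It should not be read as an estimate of bias. The gap in the data items is documented: arrival mode and pre-dose arrival vital signs are not listed. The correction is cheap enough to make without knowing the true share.

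**What to change.** 1. In Data collection, add arrival mode (ambulance, air, self-presented) and a set of vital signs on arrival before any hospital dose, for every patient.
2. In the Design section, state that the Group A patients used in the main analysis of comparisons 1, 2 and 4 are those who came by ambulance or air, matching the condition already set for D.
3. Report self-presenting patients who received the drug at the center separately, and repeat comparisons 1, 2 and 4 with them included as a sensitivity analysis.

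Treatment of any patient is unchanged. The cost is one sentence, one data field and one extra vital-sign set. A may fill somewhat more slowly or be somewhat smaller in the comparisons, and the main result would not extend to self-presenting patients. If none are enrolled, nothing is lost.

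### Contrasts of Groups B and C with A or D mix prehospital TXA with transport mode, crew or agency, and comparison 3 has no assigned TXA contrast

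*Combined protocol and SAP*

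**What the plan says.** The Design section defines the treated groups by who gives the first dose.

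- **Group A** gets both doses at the trauma center: "No TXA will be given in the field to this patient grouping". No transport mode is stated. The Comparisons section adds that eligible patients still untreated and "brought to the emergency department by agencies other than participating agencies will be assigned to the Group A".
- **Group B**, the air transport group, gets the first dose "on scene or during the flight by a licensed flight RN or licensed flight physician".
- **Group C** gets it "in the field by licensed paramedics from participating agencies". The word ambulance is not used for this group.
- **Group D** is drawn at random from five years of registry records as "200 patients, transported by ambulance or by air, with similar injury severity and hemodynamics". There is no quota, match or stratum by mode.

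The blood pressure criterion under Inclusion criteria can be met "at scene of injury, during air or/and ground medical transport, or on arrival to designated trauma centers", so both modes are eligible.

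The Comparisons section lists A with B, A with C, B with C, and A with D. The Design section also says that D is compared with all three treated groups. The Data collection and Analysis Measures sections list time from injury to TXA and time from EMS encounter to the emergency department, but not arrival mode, crew or agency. The Statistical analysis section names a t test, regression and chi-square, with no covariates.

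**The concern.** The Purpose asks whether prehospital TXA lowers mortality, blood product use and blood loss. To answer it, a contrast should change the TXA exposure and as little else as possible. Here the group that receives prehospital TXA is also defined by its crew and, for Group B, by its mode of transport. Patients who are flown may differ from those who come by road in distance, crew skills and other field care, even at equal injury severity. Choosing D to resemble the treated patients in severity and hemodynamics does not balance those factors.

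A difference in comparison 1, "Hospital/TXA vs. Air Transport/TXA", could therefore be credited to early TXA when it comes from the flight crew. Equally, a real TXA benefit could be hidden by remote injury and long transport. The B versus D and C versus D contrasts, which are the only ones that set prehospital TXA against no TXA, carry the same weakness. In comparison 3, "Air Transport/TXA vs. Paramedic/TXA", both groups are assigned a field first dose and the same second-dose pathway, so the assigned treatment does not differ.

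**Working it through.** **The plan's own figure.** The only design figure is 200 per group, from 95% confidence and a 10% margin. With a proportion of 0.5:

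- one proportion: 1.96² × 0.25 / 0.10² = 96.04, so 97
- difference of two proportions: 1.96² × 2 × 0.25 / 0.10² = 192.1, so 193 per group

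Neither is exactly 200; the second is consistent with rounding up. The present point does not depend on this figure, and more patients would not reduce the bias below.

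**What each contrast changes**

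| Contrast | TXA difference as assigned | Also changes |
|---|---|---|
| 1: A vs B | first dose in hospital vs field | mode (unless A is all air), crew |
| B vs D | none vs field first dose | mode, crew, calendar period |
| 2: A vs C | first dose in hospital vs field | crew and agency; mode if A includes air arrivals |
| C vs D | none vs field first dose | crew and agency, calendar period; mode as far as D includes air arrivals |
| 3: B vs C | none | crew; mode if C is ground |

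**Size of the mode component.** Let d be the air-minus-ground mortality difference unrelated to TXA, and f the share of the comparator (A or D) that arrived by air. Take B as all air and C as all ground; the second is a reading, not stated text. Relative to ground, the excess is d in B, 0 in C and fd in the comparator. So:

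- B minus comparator: d - fd = (1 - f)d
- C minus comparator: 0 - fd = -fd
- B minus C: d

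The documents give neither d nor f. Results for assumed values, in percentage points:

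| d | f | B contrasts | C contrasts | B vs C |
|---|---|---|---|---|
| 2 | 0% | 2.0 | 0 | 2.0 |
| 2 | 25% | 1.5 | -0.5 | 2.0 |
| 2 | 50% | 1.0 | -1.0 | 2.0 |
| 5 | 0% | 5.0 | 0 | 5.0 |
| 5 | 25% | 3.75 | -1.25 | 5.0 |
| 5 | 50% | 2.5 | -2.5 | 5.0 |

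Over a wider assumed range (d = 3 to 8, f = 0 to 30%), B contrasts carry 3 × 0.7 = 2.1 to 8 × 1 = 8.0 points, and C contrasts carry 0 to 8 × 0.3 = 2.4 points in magnitude. If d is negative, the signs reverse. For scale only, the Background cites a 1.5-point reduction in 28-day mortality from the large randomized trial. Crew and agency effects within a mode come on top and are not sized here.

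**Precision of within-mode contrasts.** Half-width = 1.96 × √[p(1 - p)(1/n₁ + 1/n₂)], assuming mortality p = 15% in each arm, so p(1 - p) = 0.1275:

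- 200 vs 200: 1.96 × √(0.1275 × 0.010) = 7.0 points
- 200 vs 100: 1.96 × √(0.1275 × 0.015) = 8.6 points
- 200 vs 50: 1.96 × √(0.1275 × 0.025) = 11.1 points
- 200 vs 20: 1.96 × √(0.1275 × 0.055) = 16.4 points

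The last three apply to comparison 1 if 50%, 25% or 10% of Group A arrive by air.

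**Effect on comparison 4.** The mode bias in A versus D is (air share of A - air share of D) × d. If D were fixed at 100 air and 100 ground while A is 25% air, then d = 2 gives (0.25 - 0.50) × 2 = -0.5 points. Drawing D by mode therefore requires comparison 4 to be stratified or reweighted.

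**The case against.** The strongest reply is that much of the mode argument is inference. Group C is described only as treated by paramedics, and no text says that Group A mixes modes. If A were all ground, mode bias in comparison 2 would be zero. That is right, and it limits the claim for comparison 2 to crew and agency, plus whatever mode imbalance A turns out to have. It does not help comparison 1, which would then carry the full gap. And because A's mode is not a listed item, the plan as written could not show which case applies.

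Second, regression is listed, and EMS-to-hospital time partly measures transport duration. Both are fair. But no model is given and mode is not a variable. In comparison 1, adjustment for mode could draw only on A's air patients, because B has no ground patients. In comparison 3, crew is the group label, so no model can separate the two.

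Third, achieved time from injury to TXA is collected and may differ between B and C, so comparison 3 may hold some timing information. This stands: what is missing is an assigned contrast. Any achieved difference in timing is entangled with mode and crew.

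Fourth, the 1.5-point benchmark is an effect of giving TXA, whereas comparison 1 sets field against hospital TXA. This also stands, so the figure serves only as a scale.

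**Conclusion.** The point holds and should be corrected. As written, comparison 1 and B versus D change TXA setting or exposure together with mode and crew. Comparison 2 and C versus D do so through crew and agency, and through mode to the extent that A or D includes air arrivals. Comparison 3 has no assigned TXA contrast.

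The size of the bias is not known from the documents. The formulas (1 - f)d and fd rest on B being all air and C all ground; the example of 1.5 and 0.5 points rests on assumed d = 2 and f = 25%.

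A reader might infer three stronger things that the documents do not support:

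- that comparison 2 has a mode bias as large as comparison 1 (at air shares below 50% it is smaller, and it may be zero);
- that the bias is shown to exceed the TXA effect (d and f are assumptions, and the benchmark is a different contrast);
- that comparison 3 will be reported as evidence of efficacy (the plan only names it by delivery route).

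**What to change.** 1. Record arrival mode and transporting crew or agency for every patient in Groups A to D.
2. Draw the 200 Group D patients in air and ground strata.
3. Compare B with air-transported A and D patients, and C with ground-transported A and D patients. Then combine the two mode-specific estimates for the overall prehospital answer.
4. Stratify comparison 4 by mode, or reweight D to A's mode mix.
5. Describe comparison 3 as a comparison of delivery by crew type, not as evidence of TXA efficacy.
6. If A has few or no air patients, state that comparison 1 cannot be read as a TXA effect, and rely on B versus air-transported D for that contrast.
7. List B versus D and C versus D in the Comparisons section, so that it agrees with the Design section.

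The cost is a small set of data fields, a stratified registry query and protocol wording, with D still at 200. The statistical cost is precision: at the assumed 15% mortality, the half-width rises from 7.0 points to about 8.6 with 100 comparators and 16.4 with 20. Differences in crew or agency within a mode would remain and should be stated as a limitation.
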